- ER+ and/or PR+ (*Note: This group of patients must have received at least 1 and up to 3 prior hormonal therapies and at least one prior chemotherapy treatment in the advanced setting. HER2+ patients in this group must have received a minimum of 2 lines of HER2-directed therapy in the advanced setting at least 1 trastuzumab-containing regimen for metastatic disease.*) This group of patients may be pre-menopausal with ovarian suppression or post-menopausal. LHRH agonists maybe used to render ovarian suppression with post-menopausal ranges of estradiol or FSH per institutional guidelines.

Section 3.2 Exclusion Criteria

19) ***Use of a prohibited concomitant medication (see Section 5.3.2 and Appendix D) that cannot be safely discontinued or substituted.***

Section 5.3.2 Prohibited Concomitant Medications

- Concomitant treatment with any medication that may cause QT prolongation or Torsades de Pointes (see Appendix D). If a patient, after study enrollment, requires use of a medication that may cause QT prolongation and/or Torsades de Pointes ***that cannot be safely substituted***, the patient must be removed from the study.

CONFIDENTIAL

STUDY DRUG: Orteronel

SCRI INNOVATIONS STUDY NUMBER: BRE 203

DATE OF PROTOCOL: Version 3.0 30 October 2013

BRE 203 CLINICAL PROTOCOL SYNOPSIS

Title of Study:	A Phase II Study with Orteronel as Monotherapy in Patients with Metastatic Breast Cancer (MBC) that Expresses the Androgen Receptor (AR)	
SCRI Innovations Protocol Number:	BRE 203	
Sponsor:	SCRI Development Innovations, LLC	
Study Duration:	The total duration of the study is planned to be 48 months (enrollment and active treatment).	Phase of Study: II
Study Centers:	This is a multicenter study to be conducted in the United States at approximately 15 sites.	
Patient Population	
This study will enroll patients with MBC who have progressed on prior hormonal/chemotherapy regimens and whose cancer expresses AR. Patients will be enrolled onto one of the 2 following cohorts based on their tumor specificity:
 
 • Cohort 1: Patients with estrogen receptor negative (ER-)/progesterone receptor negative (PR-)/ human epidermal growth factor receptor 2 negative (HER2-)/AR positive (+) MBC with 1 to 3 previous treatments for metastatic disease • Cohort 2: Postmenopausal women with ER+ and/or PR+/AR+ refractory MBC who have progressed after at least one, and up to 3, previous hormonal treatments for metastatic disease. 	
Objectives:	
Primary Objectives The primary objectives of this study are to evaluate:
 
 • Response rate (RR) and disease control rate (DCR) following treatment with orteronel in patients with refractory metastatic triple-negative breast cancer expressing AR (ER-/PR-/HER2-/AR+) • Response rate and disease control rate (DCR) following treatment with orteronel in patients with refractory ER+ and/or PR+/AR+ breast cancer. 
Secondary Objectives The secondary objectives of this study are to evaluate:
 
 • Safety and tolerability of the regimen • Measurement of changes in serum estradiol levels, total and free testosterone levels, and sex hormone binding globulin (SHBG) during treatment with orteronel • Measurement of changes in adrenocorticotropic hormone (ACTH), dehydroepiandrosterone sulfate (DHEA-S), and cortisol levels during treatment with orteronel • Progression-free survival (PFS) • Overall survival (OS). 
Exploratory Objective As an exploratory objective of this trial:
 
 • Archived tumor tissue will be assayed for the following biomarkers: loss of phosphatase and tensin homolog (PTEN) and phosphatidylinositol 3-kinase (PIK3CA) mutation. 	
Number of Patients:	Up to 86 patients are planned to be enrolled in this study (6 for the lead-in phase and 80 for continuous study treatment).	
Study Design:	
This is an open-label multicenter study to be conducted in 2 stages. All patients will receive orteronel orally (PO) at a dose of 300 mg twice daily (BID).
 
 • Lead-in Phase: The first 6 patients treated will be evaluated to confirm the safety and feasibility of this regimen. After all 6 patients complete at least 4 weeks of treatment, and if no prohibitive toxicities are identified, continuous study treatment will begin. 	

CONFIDENTIAL

STUDY DRUG: Orteronel

SCRI INNOVATIONS STUDY NUMBER: BRE 203

DATE OF PROTOCOL: Version 3.0 30 October 2013

BRE 203 CLINICAL PROTOCOL SYNOPSIS

Study Design (continued):	
 • Continuous Study Treatment: Patients will continue to be enrolled into both cohorts based on their tumor specificities with a total of 31 patients in Cohort 1 (ER-/PR-/HER2-/AR+) and 55 patients in Cohort 2 (ER+ and/or PR+/AR+). Patients will be evaluated every eight weeks for response to treatment. 
All patients who respond to treatment (complete response [CR] or partial response [PR]) or have stable disease (SD) will continue to receive orteronel until they develop progressive disease (PD) or unacceptable toxicity.

Study Drug(s), Dose, and Mode of Administration:	
Orteronel will be supplied to SCRI Innovations by Millennium Pharmaceuticals, Inc. The planned oral dose of orteronel is 300 mg BID. In the event of prohibitive toxicity, the orteronel dose may be reduced by one level to 200 mg BID.

Inclusion Criteria:	
 1. Voluntary written informed consent before performance of any study-related procedure not part of normal medical care 2. Patients must have MBC that is measurable or evaluable as defined by Response Evaluation Criteria in Solid Tumors (RECIST) v1.1 criteria (see Section 9). Patients with metastases limited to the bones are eligible. 3. Patients with breast tumors that are AR+ ($\geq 10\%$ staining by immunohistochemistry). Archived tumor tissue from a primary biopsy or metastatic lesion for centralized determination of AR expression is mandatory. If tissue is limited, the additional correlative testing is optional. If tissue is not available, a patient will not be eligible for enrollment into the study. Patients may enroll based on local laboratory AR assessment, but will need to submit tissue for confirmation at the central laboratory. 4. In addition to having AR+ tumors, patients must fit into 1 of the 2 following categories: 
 • Triple negative (ER-/PR-/HER2-) (Note: This group of patients must have received at least 1 and up to 3 prior chemotherapy regimens in the advanced setting.) • ER+ and/or PR+ (Note: This group of patients must have received at least 1 and up to 3 prior hormonal therapies and at least one prior chemotherapy treatment in the advanced setting. HER2+ patients in this group must have received a minimum of 2 lines of HER2-directed therapy in the advanced setting.) This group of patients may be pre-menopausal with ovarian suppression or post-menopausal. LHRH agonists maybe used to render ovarian suppression with post-menopausal ranges of estradiol or FSH per institutional guidelines. 5. Female or male patients ≥ 18 years-of-age 6. Eastern Cooperative Oncology Group (ECOG) performance status score of 0, 1, or 2 (see Appendix A) 7. Patient has recovered (to Grade ≤ 1) from all clinically significant toxicities related to prior antineoplastic therapies (with the exception of alopecia) 8. Adequate hematological function, defined as: 
 • Absolute neutrophil count (ANC) $\geq 1.25 \times 10^9/L$ • Platelets $\geq 75 \times 10^9/L$ • Hemoglobin $\geq 9 \text{ g/dL}$ 9. Adequate liver function, defined as: 
 • Alanine aminotransferase (ALT) and aspartate aminotransferase (AST) $\leq 2.5 \times$ the upper limit of normal (ULN), if no liver involvement or $\leq 5 \times$ ULN with liver involvement • Total bilirubin ≤ 1.5 times the upper limit of normal (ULN) (in patients with known Gilbert Syndrome, a total bilirubin $\leq 3.0 \times$ ULN, with direct bilirubin $\leq 1.5 \times$ ULN)

CONFIDENTIAL

STUDY DRUG: Orteronel

SCRI INNOVATIONS STUDY NUMBER: BRE 203

DATE OF PROTOCOL: Version 3.0 30 October 2013

BRE 203 CLINICAL PROTOCOL SYNOPSIS

Inclusion Criteria (continued):	
 10. Adequate renal function, defined as: 
 • Creatinine $\leq 1.5 \times$ ULN or creatinine clearance ≥ 40 mL/min as calculated by the Cockcroft-Gault method 11. Screening calculated LVEF of $\geq 50\%$ by echocardiogram (ECHO) or multiple-gated acquisition (MUGA) scan 12. Ability to swallow and retain oral medication 13. Male patients (even those post vasectomy) who are willing to use adequate contraceptive measures (see Appendix B) or abstain from heterosexual intercourse during the entire study treatment period and for 4 months after the last dose of study drug 14. Female patients who are not of child-bearing potential and female patients of child-bearing potential who agree to use adequate contraceptive measures (see Appendix B) or abstain from heterosexual intercourse during the entire study treatment period and for 4 months after the last dose of study drug, who are not breastfeeding, and who have had a negative serum/urine pregnancy test ≤ 7 days prior to dosing 15. Life expectancy of ≥ 3 months 16. Willingness and ability to understand the nature of this study and to comply with the study and follow-up procedures.
Exclusion Criteria:	
 1. Known hypersensitivity to orteronel or to orteronel excipients, which are listed by formulation in the Investigator Brochure 2. Patients receiving other treatment for breast cancer (includes standard hormonal therapy, chemotherapy, biologic therapy, immunotherapy, or radiation therapy). Patients receiving chronic bisphosphonate or denosumab therapy are eligible. 3. Female patients who are both lactating and breastfeeding or have a positive serum pregnancy test during the screening period. 4. Prior anti-androgen therapy 5. Use of an investigational drug ≤ 21 days or 5 half-lives (whichever is shorter) prior to the first dose of orteronel, or concurrent treatment. For investigational drugs for which 5 half-lives is less than 21 days, a minimum of 10 days between termination of the investigational drug and administration of orteronel is required. 6. Active brain metastases or leptomeningeal disease. Previously treated brain metastases are allowed provided lesions are stable for at least 3 months as documented by head CT scan or magnetic resonance imaging (MRI) of the brain. Patients must be off steroids, but anti-convulsants are allowed. 7. Patients with known adrenal insufficiency, or patients receiving treatment with ketoconazole, abiraterone, or aminoglutethimide. 8. Wide field radiotherapy (including therapeutic radioisotopes such as strontium 89) administered ≤ 28 days or limited field radiation for palliation ≤ 7 days prior to starting study drug or has not recovered from side effects of such therapy. 9. Major surgical procedures ≤ 28 days of beginning study treatment or minor surgical procedures ≤ 7 days. No waiting is required following port-a-cath placement. 10. Presence of active gastrointestinal (GI) disease or other condition that will interfere significantly with the absorption, distribution, metabolism, or excretion of oral therapy (eg, ulcerative disease, uncontrolled nausea, vomiting, diarrhea \geq Grade 2, and malabsorption syndrome).

CONFIDENTIAL

STUDY DRUG: Orteronel

SCRI INNOVATIONS STUDY NUMBER: BRE 203

DATE OF PROTOCOL: Version 3.0 30 October 2013

BRE 203 CLINICAL PROTOCOL SYNOPSIS

Exclusion Criteria: (continued)	
11. History of myocardial infarction, unstable symptomatic ischemic heart disease, ongoing arrhythmias > Grade 2 (National Cancer Institute [NCI] Common Terminology Criteria for Adverse Events [CTCAE], Version 4.0), thromboembolic events (eg, deep vein thrombosis, pulmonary embolism, or symptomatic cerebrovascular events), or any other cardiac condition (eg, pericardial effusion restrictive cardiomyopathy) within 6 months prior to first dose of study drug. Chronic stable atrial fibrillation on stable anticoagulant therapy is allowed.
 
12. New York Heart Association (NYHA) Class III or IV heart failure (Appendix C)
 
13. Electrocardiogram (ECG) abnormalities of Q-wave infarction, unless identified 6 or more months prior to screening or QTc Fridericia (F) interval >460 msec
 
14. Inadequately controlled hypertension (ie, systolic blood pressure [SBP] >160 mmHg or diastolic BP [DBP] >90 mmHg) at 2 separate measurements no more than 60 minutes apart during the Screening visit. Note: patients may be rescreened after adjustment of antihypertensive medications.
 
15. Known diagnosis of human immunodeficiency virus, active chronic hepatitis B, or C, life-threatening illness unrelated to cancer, or any serious medical or psychiatric illness that could, in the investigator's opinion, potentially interfere with participation in this study
 
16. Uncontrolled diabetes mellitus. Patients with Type II diabetes are eligible if they require only oral hypoglycemic agents and fasting blood glucose level is ≤120. Patients with Type I diabetes are eligible if their glycosylated hemoglobin (HbA_{1c}) is ≤7.
 
17. Diagnosis or treatment for another malignancy within 2 years of enrollment, with the exception of adequately treated in-situ carcinoma of the cervix, uteri, basal or squamous cell carcinoma or non-melanomatous skin cancer
 
18. Inability or unwillingness (including psychological, familial, sociological, or geographical conditions) to comply with study and/or follow-up procedures as outlined in the protocol.
 
19. Use of a prohibited concomitant medication (see Section 5.3.2 and Appendix D) that cannot be safely discontinued or substituted.

Correlative Testing:	
The following correlative testing will included:
 
 • Measurement of changes in serum estradiol levels, total and free testosterone levels, and SHBG • Measurement of changes in ACTH, DHEA-S, and cortisol levels • Biomarker testing of archived tumor tissue for loss of PTEN and PIK3CA mutations.

CONFIDENTIAL

STUDY DRUG: Orteronel

SCRI INNOVATIONS STUDY NUMBER: BRE 203

DATE OF PROTOCOL: Version 3.0 30 October 2013

BRE 203 CLINICAL PROTOCOL SYNOPSIS

Statistical Methodology:	
For patients with ER-/PR-/HER2-/AR+ tumors (Cohort 1), the expected response rate with standard anti-estrogen therapy is expected to be zero. Therefore, a response rate of at least 10% with orteronel therapy would indicate activity and would lead to further investigation. Assuming an evaluable population of 28 patients, the exact 95% confidence intervals (CIs) for a hypothesized response rate of 11% is (2.4%, 28.6%). In order to incorporate an early stopping rule, Simon's two-stage design is applied using alpha = 0.10 and power = 0.80 with comparison of the hypothesized response rate of 11% versus a conservative value of 2%. Initially, 19 patients will be enrolled in this cohort, and if no responses are observed, recruitment to this cohort will stop. Otherwise, enrollment in this cohort will continue to full accrual of 28 patients. To account for an unevaluable rate of 10%, a total of 31 patients will be enrolled in this cohort.
 
For patients with ER+ and/or PR+/AR+ tumors (Cohort 2), published data on exemestane as third-line hormonal therapy in postmenopausal women indicate a response rate of 13% and a clinical benefit rate (CR, PR, or SD >24weeks) of 30%. It is hypothesized that treatment with orteronel in this patient population will produce similar results. Assuming an evaluable population of 50 patients, the exact 95% CIs for a hypothesized response rate of 14% is (5.8%, 26.7%). In order to incorporate an early stopping rule, Simon's two-stage design is applied using alpha = 0.10 and power = 0.80 with comparison of the hypothesized response rate of 14% versus a conservative value of 5.1%. Initially, 26 patients will be enrolled in this cohort, and if one or no responses are observed, recruitment into this cohort will stop. Otherwise, enrollment in this cohort will continue to full accrual of 50 patients. To account for an unevaluable rate of 10%, a total of 55 patients will be enrolled in this cohort.

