7.3. Full Screening

Consent for the main study must be obtained ≤ 28 days prior to the initiation of study treatment. The baseline assessments described in Appendix E will be collected prior to the initiation of treatment. Baseline ECHO/MUGA should be within 28 days of treatment.

The physical examination, ECOG performance status, serum/urine pregnancy test (for women of child-bearing potential only), and complete blood counts (CBCs) should be done ≤ 7 days prior to initiation of treatment. All other assessments should be performed ≤ 4 weeks prior to initiation of treatment.

- Signed informed consent prior to any other study-related procedures
- Medical history (including assessment of baseline signs and symptoms)

CONFIDENTIAL

STUDY DRUG: Orteronel

SCRI INNOVATIONS STUDY NUMBER: BRE 203

DATE OF PROTOCOL: Version 3.0 30 October 2013

- Physical examination including measurements of height, weight, and vital signs (resting heart rate, blood pressure, respiratory rate, and oral temperature)
- Eastern Cooperative Oncology Group Performance Status (ECOG) performance status (Appendix A)
- Concomitant medication review at the time of informed consent
- Complete blood count (CBC) including 3-part differential and platelets) (may be done up to 72 hours prior to treatment)
- Comprehensive metabolic profile (CMP) (Section 7.6.3) (may be done up to 72 hours prior to treatment)
- Fasting plasma glucose, insulin, c-peptide, and HbA_{1c} (only in patients with a history of diabetes)
- Serum amylase, lipase
- Serum hormone levels: estradiol, total and free testosterone, SHBG, ACTH, DHEA-S, and cortisol
- Serum/urine pregnancy test (for women of childbearing potential only). If done within 72 hours prior to treatment, this test need not be repeated on Cycle 1 Day 1.
- 12-lead ECG
- ECHO/MUGA
- Urinalysis
- CT scan of the chest/abdomen/pelvis
- Bone scan, if clinically indicated
- CT/MRI of the brain, if clinically indicated

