9.2. Baseline Eligibility

Measurable Disease:	
Tumor lesions: Must be accurately measured in at least one dimension (longest diameter in the plane of measurement is to be recorded) with a minimum size of:
 
• 10 mm by CT scan (CT scan slice thickness no greater than 5 mm).• 10 mm caliper measurement by clinical exam (lesions that cannot be accurately measured with calipers should be recorded as non-measurable).• 20 mm by chest x-ray. 
Skin lesions: Documentation by color photography, including a ruler to estimate the size of the lesion, is recommended.
 
Malignant lymph nodes: To be considered pathologically enlarged and measurable, a lymph node must be >15 mm in short axis when assessed by CT scan. At baseline and in follow-up, only the short axis will be measured and followed.

Non-Measurable Disease:	All other lesions, including small lesions (longest diameter <10 mm or pathological lymph nodes with >10 - to <15 -mm short axis) as well as truly non-measurable lesions. Lesions considered truly non-measurable include: leptomeningeal disease, ascites, pleural or pericardial effusion, inflammatory breast disease, lymphangitic involvement of skin or lung, abdominal masses, abdominal organomegaly identified by physical exam that is not measurable by reproducible imaging requirements.
Target Lesions:	
The most reproducible measurable lesions, up to a maximum of 2 lesions per organ and 5 lesions in total, representative of all involved organs should be identified as target lesions and recorded and measured at baseline.
 
Target lesions should be selected on the basis of their size (lesions with the longest diameter), should be representative of all involved organs, and in addition should be those that lend themselves to reproducible repeated measurements. Pathological nodes which are defined as measurable and that may be identified as target lesions must meet the criterion of a short axis of >15 mm by CT scan.
 
A sum of the diameters (longest for non-nodal lesions, short axis for nodal lesions) for all target lesions will be calculated and reported as the baseline sum diameters. If lymph nodes are to be included in the sum, then as noted above, only the short axis is added into the sum. The baseline sum diameters will be used as reference to further characterize any objective tumor response.

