9.2.1. Guidelines for Evaluation of Measurable Disease

All measurements should be taken and recorded in metric notation, using a ruler or calipers. All baseline evaluations should be performed as closely as possible to the beginning of treatment, as per protocol screening requirements.

CONFIDENTIAL

STUDY DRUG: Orteronel

SCRI INNOVATIONS STUDY NUMBER: BRE 203

DATE OF PROTOCOL: Version 3.0 30 October 2013

The same method of assessment and the same technique should be used to characterize each identified and reported lesion at baseline and during follow-up. Imaging-based evaluation is preferred to evaluation by clinical examination when both methods have been used to assess the anti-tumor effect of a treatment.

Clinical Lesions:	Clinical lesions will only be considered measurable when they are superficial (e.g., skin nodules and palpable lymph nodes). In the case of skin lesions, documentation by color photography, including a ruler to estimate the size of the lesion, is recommended.
Chest X-ray:	Lesions on chest X-ray are acceptable as measurable lesions when they are clearly defined and surrounded by aerated lung. However, CT is preferable.
Conventional CT and MRI:	CT and MRI are the best currently available and reproducible methods to measure target lesions selected for response assessment. Conventional CT and MRI should be performed with cuts of 10 mm or less in slice thickness, contiguously. Spiral CT scan should be performed using a 5-mm contiguous reconstruction algorithm. This applies to tumors of the chest, abdomen, and pelvis. Head and neck tumors and those of extremities usually require specific protocols.
Ultrasound:	When the primary trial endpoint is objective response, ultrasound should not be used to measure tumor lesions. It is, however, a possible alternative to clinical measurements of superficial palpable lymph nodes, subcutaneous lesions, and thyroid nodules. Ultrasound may also be useful to confirm the complete disappearance of superficial lesions usually assessed by clinical examination.
Endoscopy and Laparoscopy:	Use of endoscopy and laparoscopy for objective tumor evaluation has not yet been fully and widely validated. Therefore, use of these techniques for objective tumor response should be restricted to validation purposes in specialized centers. Such techniques can be useful in confirming complete pathological response when biopsies are obtained.

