9.2.2. Response Criteria

Evaluation of Target Lesions

Complete Response (CR): Disappearance of all target lesions.

Partial Response (PR): At least a 30% decrease in the sum of the longest diameter (LD) of target lesions, taking as reference the baseline sum LD.

Stable Disease (SD): Neither sufficient shrinkage to qualify for PR nor sufficient increase to qualify for PD, taking as reference the smallest (nadir) sum LD since the treatment started.

Progressive Disease (PD): At least a 20% increase in the sum of the LD of target lesions, taking as reference the smallest (nadir) sum since the treatment started, or the appearance of one or more new lesions. Requires not only 20% increase, but absolute increase of a minimum of 5 mm over sum.

Evaluation of Non-Target Lesions

Complete Response (CR): Disappearance of all non-target lesions and normalization of tumor markers. All lymph nodes must be non-pathological in size (<10 mm short axis).

Stable Disease (SD): Persistence of one or more non-target lesions and/or persistence of tumor marker level above the normal limits.

Progressive Disease (PD): Appearance of one or more new lesions and/or unequivocal progression of existing non-target lesions. When the patient also has measurable disease, to achieve “unequivocal progression” on the basis of the non-target disease, there must be an overall level of substantial worsening in non-target disease such that, even in presence of SD or PR in the target disease, the overall tumor burden has increased sufficiently to merit discontinuation of therapy.

Evaluation of Best Overall Response

The best overall response is the best response recorded from the start of the treatment until disease progression/recurrence (taking as reference for progressive disease the smallest measurements recorded since the treatment started). In general, the patient's best response assignment will depend on the achievement of both measurement and confirmation criteria.

Confirmation of response (by repeat scans after 4 weeks or as specified in the protocol) is required for trials in which response rate is the primary endpoint, but is not required in randomized trials or trials with primary survival endpoints (i.e., where response is not a primary endpoint).

CONFIDENTIAL

STUDY DRUG: Orteronel

SCRI INNOVATIONS STUDY NUMBER: BRE 203

DATE OF PROTOCOL: Version 3.0 30 October 2013

Target Lesions	Non-Target Lesions	New Lesions	Overall Response
CR	CR	NO	CR
CR	SD	NO	PR
CR	NE	NO	PR

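### A target lesion can be irradiated between its baseline CT and the first dose, and its shrinkage then counts toward an orteronel partial response

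*Combined protocol and SAP*

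**What the plan says.** **Radiation before treatment.** Exclusion 8 (Synopsis and Section 3.2) bars "limited field radiation for palliation ≤ 7 days prior to starting study drug". Day -8 is therefore the latest permitted day. Wide-field radiotherapy is barred for 28 days.

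**Age of the baseline CT.** Section 7.3 lists the assessments that must fall within 7 days of treatment, and CT is not among them. It comes under the general rule: "All other assessments should be performed ≤ 4 weeks prior to initiation of treatment". Appendix E sets no tighter limit.

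**Timing advice.** Section 9.2.1 adds: "All baseline evaluations should be performed as closely as possible to the beginning of treatment, as per protocol screening requirements". This refers back to the same 4-week window and does not mention earlier treatment.

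**Choice of target lesions.** Section 9.2 takes "The most reproducible measurable lesions, up to a maximum of 2 lesions per organ and 5 lesions in total", selected on size, representativeness and reproducibility. Irradiation is not mentioned.

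**Partial response.** Section 9.2.2 defines it as "At least a 30% decrease in the sum of the longest diameter (LD) of target lesions, taking as reference the baseline sum LD".

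**Decision rules (Section 10.4).** Cohort 1 stops at 0 responses in 19 and succeeds at 2 or more in 28. Cohort 2 stops at 0 or 1 in 26 and succeeds at 5 or more in 50.

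**The concern.** The radiation rule and the scan rule both count back from the first dose, but neither refers to the other. In an eligible patient the order can be baseline CT, then palliative radiation to a measured lesion, then orteronel. The reference sum in that case predates the radiation, and the first on-study scan reflects radiation and drug together.

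The trial has no control arm, so nothing offsets a response that belongs to the radiation. The cut-offs are low enough for a single misattributed PR to keep a cohort open at the interim look or take it over the success threshold. No other provision closes the gap:

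- Exclusion 2 covers "Patients receiving other treatment for breast cancer (includes standard hormonal therapy, chemotherapy, biologic therapy, immunotherapy, or radiation therapy", which concerns treatment in progress. It sets no interval and no link to the scan.
- A rule applied only when lesions are selected would miss a lesion irradiated afterwards.
- The confirmatory scan in Section 9.2.2 does not help if the radiation shrinkage persists.

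**Working it through.** **1. Day arithmetic**

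| Baseline CT on | Last permitted limited-field fraction | Days between |
|---|---|---|
| day -28 | day -8 | 28 - 8 = 20 |
| day -14 | day -8 | 14 - 8 = 6 |
| day -8 or later | day -8 | none |

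The wide-field exclusion (28 days) is as long as the scan window, so wide-field treatment cannot follow the baseline CT. Only the limited-field route is open.

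**2. The plan's own error rates**

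Inputs from Sections 10.3 and 10.4 are:

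- Cohort 1: null 2%, alternative 11%, 19 then 28 patients
- Cohort 2: null 5.1%, alternative 14%, 26 then 50 patients
- alpha 0.10 and power 0.80 in both

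With response probability p, stage 1 size n1, stopping bound r1, final size n and success bound r:

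P(success) = sum over x > r1 of Bin(x; n1, p) × P(X2 ≥ r - x), where X2 ~ Bin(n - n1, p).

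For Cohort 1 this reduces to 1 - (1-p)^19 - 19p(1-p)^18 × (1-p)^9. At p = 0.02 that is 1 - 0.6812 - 0.2642 × 0.8337 = 0.0985.

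| | Type I error | Power |
|---|---|---|
| Cohort 1 | 0.0985 | 0.8009 |
| Cohort 2 | 0.0973 | 0.8057 |

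Both designs reproduce, and neither has much room below 0.10.

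**3. Illustration of size**

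The documents give no rate of false PRs. Assume 5% of patients have a lesion irradiated after the baseline CT, and that 5%, 10% or 20% of those reach -30% on the sum for that reason. This gives 0.25%, 0.5% or 1% of all patients. Adding these to the null rate and applying the same formula:

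| False PRs | Cohort 1: p | P(success) | Cohort 2: p | P(success) |
|---|---|---|---|---|
| 0 | 2.00% | 0.0985 | 5.10% | 0.0973 |
| 0.25% | 2.25% | 0.1198 | 5.35% | 0.1131 |
| 0.5% | 2.50% | 0.1421 | 5.60% | 0.1300 |
| 1% | 3.00% | 0.1889 | 6.10% | 0.1671 |

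The expected number of false PRs is small: 28 × 0.0025 = 0.07 to 28 × 0.01 = 0.28 in Cohort 1, and 50 × 0.0025 = 0.125 to 50 × 0.01 = 0.50 in Cohort 2.

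**4. If the true response rate in Cohort 1 is zero**

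Here p is the false-PR rate alone. At p = 0.01, P(success) = 1 - 0.8262 - 0.1586 × 0.9135 = 0.029. The results are 0.0021, 0.0079 and 0.0290 for 0.25%, 0.5% and 1%.

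**The case against.** Several conditions must coincide. The radiation must be limited-field and palliative, with its side effects resolved, and must hit a CT-measured lesion. That lesion must carry enough of a sum of up to five to bring it down by 30%. There must be no new lesion and no progression elsewhere, and the response must be confirmed. An irradiated site that is not measurable cannot produce a PR through the target sum. The 20-day gap also needs a CT on day -28, and Section 9.2.1 pushes scans later than that. All of this stands. It makes the event uncommon but does not make it impossible under the rules as written.

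The rates in the illustration have no source in the documents. That also stands, and they carry no weight beyond showing sensitivity.

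Section 5.3.1 permits palliative radiation during treatment, again with no rule for response assessment. One rule on irradiated target lesions could cover both periods, but the protocol contains neither.

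A reader might infer two stronger points that the documents do not support:

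- **Investigational drugs.** Exclusion 5 bars "Use of an investigational drug ≤ 21 days or 5 half-lives (whichever is shorter) prior to the first dose of orteronel" and, where 5 half-lives is under 21 days, says "a minimum of 10 days between termination of the investigational drug and administration of orteronel is required". A drug could thus be stopped about 18 days after a day -28 CT (28 - 10). That is day arithmetic only. Nothing in the documents suggests that a patient would stop such a drug after the CT and then owe it a confirmed 30% fall.
- **An inactive drug likely to be called active.** The 12.0-18.9% in Cohort 1 arises only on top of a 2% true response rate. Section 10.3 puts the response rate expected with standard anti-estrogen therapy at zero and calls 2% conservative. If orteronel's own true response rate were zero, the figures would be 0.2-2.9%, well below 10%.

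**Conclusion.** The gap is real and confined to limited-field radiation. The screening windows let a measured lesion be irradiated after its baseline scan and before the first dose, and the response definition credits the shrinkage to orteronel. This follows from the text and does not depend on how often it happens.

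The size is uncertain and probably small. Under the assumed 0.25-1% of false PRs on top of the design nulls, type I error would exceed the stated 0.10 in both cohorts: 12.0-18.9% in Cohort 1 and 11.3-16.7% in Cohort 2. This shows how sensitive low cut-offs are. It does not estimate what will occur, and it does not show that a Cohort 1 with no true responses would be likely to succeed. The correction is worth making because it removes an avoidable bias in the primary endpoint at little cost.

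**What to change.** Add to Section 9.2, under target lesions: a lesion irradiated between its baseline scan and the first dose may not be a target lesion and is recorded as non-target, unless baseline imaging is repeated after the radiation and within the 4-week window.

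**Cost.** One sentence, and no compulsory extra scan. A few patients lose a target lesion. A patient with no other measurable lesion cannot reach PR by the target-lesion criterion unless re-imaged.

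**What is not needed.** Requiring the CT to follow the last dose of every earlier anticancer treatment would go further than this gap warrants. It could force a repeat of a scan, still within 4 weeks, that documented progression on standard therapy. Washout intervals, eligibility, the sample size and the decision rules stay as they are.
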